state or marrow CR within 12 weeks of treatment. The method of Thall, Simon and Estey[26] will be used to monitor efficacy and safety. The design software Multc Lean Desktop (version 2.1) developed by the Department of Biostatistics at M. D. Anderson Cancer Center (MDACC) was used to generate the stopping boundaries and the operating characteristics table for futility and toxicity monitoring.

Futility

We assume a target response rate of 25% and a response rate of 15% or lower will be considered not desirable. The study will be stopped early if the data suggest that:

$$\Pr(P_E > P_H + 0.10 | \text{data}) < 0.025$$

where P_E and P_H are the response rates for daratumumab in combination with venetoclax and historical treatment, respectively. That is, if at any time during the study we determine that there is less than 2.5% chance that the response rate improves over historical rate by more than 10%, the trial will be stopped due to futility. P_E and P_H are assumed to follow a prior of Beta (0.3, 1.7) and Beta (150, 850), respectively. The stopping boundaries for efficacy based on these assumptions and monitoring conditions are provided in **Table 4**. We will apply these stopping boundaries in cohort sizes of 6.

Table 4. Stopping boundaries for futility monitoring

# of patients evaluated for response	Stop the trial if # of patients with response is less than or equal to:
6-12	0
18	0-1
24	0-2
30	0-3
36	0-4

Toxicity

Unacceptable toxicities are defined as any treatment-related grade 3 or higher non-hematologic toxicities that occur within the first 12 weeks of treatment. Denote the probability of toxicity by P_T . We assume as a priori, $P_T \sim \text{beta}(0.6, 1.4)$. Our stopping rule is given by the following probability statement:

$$\Pr(P_T > 0.30 | \text{data}) > 0.975.$$

That is, we will stop the trial for new patient enrollment if at any time during the study, we determine that there is more than 97.5% chance that the unacceptable toxicity rate is more than 30%. This toxicity monitoring rule will be applied after the first 6 patients have been enrolled and evaluated, and then in cohort size of 6. Stopping boundaries corresponding to this stopping rule are listed in **Table 5**. The operating characteristics for efficacy and toxicity monitoring are summarized in **Table 6**.

Table 5. Early stopping boundaries for toxicity monitoring

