Adverse event is any untoward medical occurrence that may present during treatment with a pharmaceutical product but which does not necessarily have a causal relationship with this treatment. Adverse drug reaction is a response to a drug which is noxious and unintended and which occurs at doses normally used in man for prophylaxis, diagnosis, or therapy of disease or for the modification of physiologic function. The Investigator or physician designee is responsible for verifying and providing source documentation for all adverse events, and assigning attribution for each event on all subjects enrolled on this study.

For this protocol, adverse events and protocol specific data will be entered into PDMS/CORe. PDMS/CORe will be used as the electronic case report form for this protocol.

Only unexpected AEs related to the study drug will be recorded in the Case Report Form (CRF). Expected events during leukemia therapy are:

1. Myelosuppression related events (due to disease or leukemia therapy)

- a) febrile or infection episodes not requiring management in the intensive care unit
- b) epistaxis or bleeding except for catastrophic CNS or pulmonary hemorrhage
- c) anemia, neutropenia, lymphopenia, thrombocytopenia, leukopenia, leukocytosis

2. Disease related events

- a) symptoms associated with anemia
 - i. fatigue
 - ii. weakness
 - iii. shortness of breath
- b) electrolyte abnormalities (sodium, potassium, bicarbonate, CO₂, magnesium)
- c) chemistry abnormalities (LDH, phosphorus, calcium, BUN, protein, albumin, uric acid, alkaline phosphatase, glucose)
- d) coagulation abnormalities
- e) disease specific therapy (induction, maintenance, salvage, or stem cell therapy)
- f) alopecia

- g) bone, joint, or muscle pain
- h) liver function test abnormalities associated with infection or disease progression
- i) disease progression

3. General therapy related events

- a) catheter related events
- b) renal failure related to tumor lysis syndrome or antibiotic/antifungal therapy
- c) rash related to antibiotic use
- d) abnormal hematologic values will not be recorded on the CRF. For abnormal chemical values grade 3 or 4, the apogee will be reported per course in the CRF.

B. Serious Adverse Event (SAE) Reporting

An adverse event or suspected adverse reaction is considered “serious” if, in the view of either the investigator or the supporter, it results in any of the following outcomes:

- Death

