- **Serious adverse events will be captured from the time of the first protocol-specific intervention, until 30 days after the last study treatment/intervention, unless the participant withdraws consent. Serious adverse events must be followed until clinical recovery is complete and laboratory tests have returned to baseline, progression of the event has stabilized, or there has been acceptable resolution of the event.**
- **Additionally, any serious adverse events that occur after the 30 day time period that are related to the study treatment must be reported to the IND Office. This may include the development of a secondary malignancy.**

NOTE: DEATH FOR ANY REASON SHOULD BE REPORTED AS A SERIOUS ADVERSE EVENT.

C. Reporting to FDA

- Serious adverse events will be forwarded to FDA by the IND Supporter (Safety Project Manager IND Office) according to 21 CFR 312.32.
- It is the responsibility of the PI and the research team to ensure that serious adverse events are reported according to the Code of Federal Regulations, Good Clinical Practices, the protocol guidelines, the supporter's guidelines, and Institutional Review Board policy.

13. Reporting SAE to Janssen Scientific Affairs, LLC

A. Management of Safety Data

This Study has been designated as an interventional study. As such, all adverse events for Janssen Medicinal Products regardless of causality and special situations excluding those from subjects not exposed to a Janssen Medicinal Product and product quality complaints with or without an adverse event as described in this Exhibit will be reported from the time a subject has signed and dated an Informed Consent Form (ICF) until completion of the subject's last study-related procedure (which may include contact for follow-up safety). Serious adverse events will be reported for 30 days after the last dose of study drug.

For the purposes of this study, the Janssen medicinal product is: DARZALEX™ (daratumumab)

B. Adverse Events of Special Interest

Adverse events of special interest are events that Janssen Scientific Affairs, LLC is actively monitoring as a result of a previously identified signal (even if non-serious).

These adverse events are:

- Infusion reactions \geq Grade 3
- Infections \geq Grade 4
- Cytopenias \geq Grade 4 (Only related to Daratumumab)
- Tumor Lysis Syndrome
- Other Malignancies
- Intravascular Hemolysis – All Grades

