The type of birth control used must be discussed with, and approved by, the study doctor before beginning the study. Approved birth control must be in the form of oral, injected or implanted methods (e.g., placement of an intrauterine device or intrauterine system, condom with spermicidal foam/gel/film/cream/suppository, diaphragm, cervical/vault caps with spermicidal foam/gel/film/cream/suppository, male partner sterilization, or abstinence).

All initial reports of pregnancy must be reported to Janssen Scientific Affairs, LLC by the PRINCIPAL INVESTIGATOR within 24 hours of becoming aware of the event using the Serious Adverse Event Form. Abnormal pregnancy outcomes (e.g. spontaneous abortion, fetal death, stillbirth, congenital anomaly, ectopic pregnancy) are considered serious adverse events and must be reported using the Serious Adverse Event Form.

Any subject who becomes pregnant during the study must be promptly withdrawn from the study and discontinue further study treatment.

Because the effect of the Janssen medicinal product on sperm is unknown, pregnancies in partners of male subjects exposed to a Janssen medicinal product will be reported by the PRINCIPAL INVESTIGATOR within 24 hours of their knowledge of the event using the Serious Adverse Event Form. Depending on local legislation this may require prior consent of the partner.

Follow-up information regarding the outcome of the pregnancy and any postnatal sequelae in the infant will be required.

F. Maintenance of Safety Information

All safety data should be maintained in a clinical database in a retrievable format. The PRINCIPAL INVESTIGATOR shall provide all adverse events, both serious and non-serious, in report format. However, in certain circumstances more frequent provision of safety data may be necessary, e.g. to fulfill a regulatory request, and as such the data shall be made available within a reasonable timeframe at Janssen Scientific Affairs, LLC request.

G. Procedures for Reporting Safety Data and Product Quality Complaints (PQCs) for Janssen Medicinal Products to Janssen Scientific Affairs, LLC

All adverse events and special situations, whether serious or non-serious, related or not related, following exposure to a Janssen medicinal product are to be documented by the investigator and recorded in the CRF and in the subject's source records. Investigators must record in the CRF their opinion concerning the relationship of the adverse event to a Janssen medicinal product.

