Physical exam	Including neurological exam	X	Symptom and disease directed exam as clinically indicated				
Vital signs	Vital signs (blood pressure, heart rate, temperature) measured in sitting position. On C1D1: immediately before the start of daratumumab infusion; at 0.5, 1, 1.5, 2, 3.5 hr after start of infusion; at end of infusion; 0.5, 1 hr after end of infusion.	X	X	X	X		

	Notes	Screening Phase	Treatment (Cycles 1-2)	Treatment (Cycles 3-6)	Treatment (Cycles 7+)	EoT	Follow-up w/Response						
		within 14 days	D1, D8, D15, D22	D1, D15	D1	(28-35 days after last dose)	(after EoT)						
	For all other infusions , vital signs measured immediately before start and at end of daratumumab infusion.												
Laboratory Assessments													
Serum Pregnancy test ^b	For women of childbearing potential only, within 14 days of first dose and again within 24 hrs of first dose.	X	X	Q4 Weeks									
Hematology	Includes WBC with differential, hemoglobin, platelet	X	X	X	X	X	X*						
Serum Chemistry	Includes Na, K, Bicarbonate, BUN, creatinine, AST and/or ALT, Ca, Phosphorus, total bilirubin	X	D1, D15	D1	X	X	X						
Bone Marrow aspirate and/or biopsy	Morphology, immunohistochemistry/immuno fluorescence/flow cytometry as appropriate. With differential and estimate of cellularity.	X	C2, D1 (+/- 2 days)	C3, D1 every cycle until response (+/- 2 days) After that, according to investigator's discretion									
Blood type assessment and wallet card		X											
CMV screening		X	Every 2 weeks		Every 4 weeks		Every 4-12 weeks						
HBV, HCV, HIV testing		X ^e											
HBV DNA testing			X ^f										
Ongoing Subject Review													
Adverse Events	See Section 12 for detailed instructions		Continuous from the time of signing of ICF until 30 days after last dose of last study drug. Any adverse event ongoing at EoT will be followed until the event resolves, stabilizes or returns to baseline status.										
Concomitant Medications ^d			Continuous from the time of signing the ICF until 30 days after last dose of study drug.										

	Notes	Screening Phase	Treatment (Cycles 1-2)	Treatment (Cycles 3-6)	Treatment (Cycles 7+)	EoT	Follow-up w/Response
		within 14 days	D1, D8, D15, D22	D1, D15	D1	(28-35 days after last dose)	(after EoT)
Survival Status (no response)	Telephone interview lasting approximately 5 minutes: Following EoT: one time each month for the first year; every six months during the second year; one time per year thereafter						

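### Section 12.A keeps expected adverse events out of the CRF, contradicting Section 13.G and leaving out events that the toxicity stopping rule counts; the supplied text names no data source for the Table 5 count

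*Combined protocol and SAP*

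**What the plan says.** Two sections give different rules for what goes into the CRF.

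- Section 12.A: "Only unexpected AEs related to the study drug will be recorded in the Case Report Form (CRF". It then lists events regarded as expected during leukemia therapy. The list includes "febrile or infection episodes not requiring management in the intensive care unit" and "epistaxis or bleeding except for catastrophic CNS or pulmonary hemorrhage". The same section makes PDMS/CORe the electronic CRF.
- Section 13.G says that all adverse events, serious or not, "related or not related, following exposure to a Janssen medicinal product are to be documented by the investigator and recorded in the CRF".

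Section 11 (Toxicity) defines what the stopping rule counts: "Unacceptable toxicities are defined as any treatment-related grade 3 or higher non-hematologic toxicities that occur within the first 12 weeks of treatment". It sets no condition on expectedness. Table 5 stops the trial at 5, 8, 10, 13, 15 or 17 patients with toxicity at 6, 12, 18, 24, 30 or 36 patients.

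The adverse-event row of Table 7 directs staff to the narrower rule: "See Section 12 for detailed instructions". Section 5 has the IND Office and the Principal Investigator review interim safety data but does not say which dataset supplies the Table 5 count.

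**The concern.** All patients are planned to receive daratumumab, so 12.A and 13.G apply to the same patients and the same form, and both cannot be followed. The 12.A set is also narrower than the set the stopping rule needs. An event can be treatment-related, grade 3, non-hematologic and within 12 weeks, and still be on the expected list.

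The same patients could therefore give different Table 5 counts depending on which section the site follows. The error runs one way, because leaving out a qualifying event can lower the count but never raise it. If the CRF feeds the count, the toxicity stop is weaker than Table 6 implies. If the CRF also feeds the safety summaries in the Analysis Plan, those are biased low.

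**Working it through.** **1. Which qualifying events have a recording route if 12.A is followed**

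| Event (treatment-related, non-hematologic, grade 3 or above, first 12 weeks) | Route |
|---|---|
| Unexpected | CRF, under 12.A |
| Serious, expected or not | SAE report to the IND Office (12.B) |
| Grade 3 or above infusion reaction; tumor lysis syndrome; infection of grade 4 or above | SAE form to the company as a special-interest event (13.B) |
| Grade 3 or 4 chemistry value | CRF, under 12.A: "For abnormal chemical values grade 3 or 4, the apogee will be reported per course in the CRF" |
| Expected, non-serious, none of the above (for example a grade 3 infection or bleed attributed to treatment) | Source documents only |

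The last row is the gap. The special-interest list does not close it, because infections enter only from grade 4. The supplied text does not link the SAE or special-interest routes to the Table 5 count.

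**2. Reproducing the plan's figures**

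Inputs from Section 11: prior Beta(0.6, 1.4); stop if Pr(P_T > 0.30 | data) > 0.975; looks every 6 patients to 36. With x toxicities in n patients the posterior is Beta(0.6 + x, 1.4 + n - x). The boundary is the smallest x that passes 0.975.

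| n | Boundary x | Probability at x - 1 | Probability at x |
|---|---|---|---|
| 6 | 5 | 0.9449 | 0.9908 |
| 12 | 8 | 0.9692 | 0.9924 |
| 18 | 10 | 0.9514 | 0.9831 |
| 24 | 13 | 0.9742 | 0.9906 |
| 30 | 15 | 0.9666 | 0.9860 |
| 36 | 17 | 0.9603 | 0.9817 |

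These match Table 5 exactly. With the Table 4 futility boundaries added, response and toxicity independent and the n = 36 look included, exact binomial recursion also reproduces all twelve stopping probabilities in Table 6 (for example 0.7950 at response 0.25 and toxicity 0.50). Those figures assume that every patient with a qualifying toxicity is counted.

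**3. Effect of incomplete recording (illustration)**

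The documents give no recorded share, so 50% to 100% is assumed. Only the toxicity rule is applied here, so these results are not comparable with Table 6. At each look, the distribution of the recorded count is convolved with Binomial(6, q), and counts at or above the Table 5 boundary are removed. The stopping probability is 1 minus the mass left after n = 36. Mean enrolment is 6 times the sum of the probabilities of still being open after 0, 6, 12, 18, 24 and 30 patients.

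*Patient level:* q = true rate x share of affected patients recorded. For example, 0.50 x 0.90 = 0.45.

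*Event level:* events per patient are Poisson with mean -ln(1 - true rate), and q = 1 - exp(-mean x share of events recorded). For example, the mean is -ln(0.5) = 0.693, and q = 1 - exp(-0.693 x 0.90) = 0.464. The loss is milder because a patient drops out only if all of that patient's qualifying events are unrecorded.

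| Share recorded | Stop, true 50%, patient level | Mean enrolment, same case | Stop, true 40%, patient level | Stop, true 50%, event level |
|---|---|---|---|---|
| 100% | 0.7398 | 24.5 | 0.3055 | 0.7398 |
| 95% | 0.6382 | 26.5 | 0.2301 | 0.6696 |
| 90% | 0.5262 | 28.5 | 0.1664 | 0.5902 |
| 75% | 0.2130 | 33.0 | 0.0489 | 0.3275 |
| 50% | 0.0133 | 35.7 | 0.0029 | 0.0412 |

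**The case against.** The strongest reply is that the harm is inferred. No passage says that the Table 5 count is taken from the CRF. Section 12.A itself requires source documentation and attribution for every adverse event, so a count made from source records would be complete. The gap is also narrow. Hospital admission or medical importance makes an event serious, and serious events reach the IND Office, which conducts the interim review, whatever their expectedness or attribution. Infection and bleeding are listed as consequences of myelosuppression from disease or therapy, and an episode attributed to disease is not counted by the stopping rule in any case. Section 12 also defers to Appendix D, whose text was not available and which might settle the question. Finally, the recorded share is assumed, and nothing in the documents points to 75% or 50%.

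Much of this stands. The loss may be small, it arises only if 12.A prevails and the CRF is the source, and the table above should not be read as a forecast. Three things remain. The sections contradict each other on their face, and Appendix D could not remove that. The supplied text does not require the count to be made from source records. And the form to which Table 7 and 12.A lead staff is the restricted one.

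**Conclusion.** The concern holds. Sections 12.A and 13.G conflict on the content of the CRF, 12.A covers less than the event defined in Section 11, and the supplied text names no source for the Table 5 count. Table 5 is correctly computed; the defect is in data capture.

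The size of the loss cannot be determined from the documents. Its direction can: any omission weakens the toxicity stop. Even modest loss would matter. At a true rate of 50%, recording 90% instead of 100% lowers the rule's stopping probability by 0.21 at patient level (0.740 to 0.526) or 0.15 at event level (0.740 to 0.590). This rests on the assumed shares, on 12.A being the rule followed, on the CRF being the source, and on Appendix D not closing the gap. The point should be fixed; confidence is medium because Appendix D was not seen.

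**What to change.** Reconcile 12.A with 13.G, and put the same statement in 12.A and in Section 11, for example:

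> Each non-hematologic adverse event of grade 3 or above that is attributed to study treatment and occurs in the first 12 weeks is entered in the CRF, whether expected or unexpected, with its grade, attribution and onset date. The Table 5 count is made from these CRF entries.

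If an exemption is kept for hematologic events, or for disease-related events not attributed to treatment, word it identically in 12.A and 13.G. Check Appendix D against the agreed text. Also state how the expected-event list in 12.A relates to 13.C, which judges expectedness for daratumumab by the Investigator's Brochure.

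The cost is a wording amendment and modest extra data entry for at most 36 patients, since 12.A already requires attribution and source documentation for all adverse events. Boundaries, looks and sample size do not change.

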All study procedures are presented in [**Table 7. Schedule of Study Events**](#). Results of all assessments will be recorded on the appropriate CRF. Study treatment should be initiated within 72 hours after registration. One cycle is 4 weeks (28 days) in duration. The start of each cycle may occur +/- 3 days of the scheduled day in order to accommodate the schedule of the site or subject.

Beyond day 1, safety laboratory evaluations can be done according to the time window provided for subsequent dosing.

i. Screening Procedures

The investigator will inform each prospective subject of the nature of the study, explain the potential risks, and obtain written informed consent from the subject

prior to performing any study-related procedures and prior to the administration of study drug.

The results of the screening evaluation must meet the inclusion/exclusion criteria for the subject to be entered into the study. Thus the investigator must review the results of diagnostic testing (bone marrow biopsy/aspirate and serum pregnancy test [if applicable], and clinical laboratory tests), and the results of that screening testing must meet the inclusion/exclusion criteria for the subject to be enrolled into the study.

ii. Daratumumab Interference with Indirect Antiglobulin Test (IAT) results

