Follow-Up procedures will occur after End of Treatment (EoT). The subject will be contacted regularly by telephone, approximately 1 time each month for the first year after the EoT visit, then every 6 months during the second year, and then 1 time each year after that to determine survival status. Any adverse events ongoing when subject stops the study will be followed by the Investigator until the event resolves, stabilizes, or returns to baseline status.

For the subject with response, the Follow-Up procedures include blood draw for CBC/Chemistry once per month for first 2 years after the EoT visit. Patients with continued response will be moved from this study to be followed under Leukemia Department umbrella protocols.

End of Treatment

At the time of discontinuation of treatment for any reason, subjects will report to the study site. EoT assessments may be performed at the discretion of the investigator. This assessment is to be completed 28-35 days after last dose administered.

9. Criteria for Response for Acute Leukemias and MDS

International Working Group Criteria[23, 24] will be used to define response. In general responses will include

1. Complete remission (CR): The patient must be free of all symptoms related to leukemia and have an absolute neutrophil count $\geq 1.0 \times 10^9/L$, platelet count $\geq 100 \times 10^9/L$, and normal bone marrow differential ($\leq 5\%$ blasts).
2. Complete remission without platelet recovery (CRp): As per CR but platelet count $< 100 \times 10^9/L$.
3. Partial remission (PR): CR with 6 to 25% abnormal cells in the marrow or 50% decrease in bone marrow blasts.
4. Marrow CR: Bone marrow: $\leq 5\%$ myeloblasts and decrease by $\geq 50\%$ over pre-treatment (MDS only)
5. Morphologic leukemia-free state: Normal marrow differential ($<5\%$ blasts); absolute neutrophil count and platelet counts are not considered. (AML only)

6. Hematologic Improvement (HI): HI should be described by the number of individual, positively affected cell lines (e.g. HI-E; HI-E + HI-N; HI-E + HI-P +HI-N)
 - a) Erythroid response (HI-E):
 - Major response: For patients with pretreatment hemoglobin less than 11 g/dL, greater than 2 g/dL increase in hemoglobin; for RBC transfusion-dependent subjects, transfusion independence.
 - Minor response: For patients with pretreatment hemoglobin less than 11 g/dL, 1 to 2 g/dL increase in hemoglobin; for RBC transfusion-dependent patients, 50% decrease in transfusion requirements.

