# of patients (in cohort size of 6, starting from the 6 th patient)	Stop the trial if there are this many patients with toxicities:
6	5-6
12	8-12
18	10-18
24	13-24
30	15-30
36	17-36

Table 6. Operating characteristics for efficacy and toxicity monitoring

True response rate	True toxicity rate	Prob (stop the trial early)	Average number of patients treated
0.15	0.10	0.5752	25.3
	0.30	0.5959	24.7
	0.40	0.7049	22.3
	0.50	0.8895	17.3
0.25	0.10	0.2119	35.0
	0.30	0.2504	34.1
	0.40	0.4526	30.2
	0.50	0.7950	22.3
0.30	0.10	0.1282	37.6
	0.30	0.1708	36.6
	0.40	0.3945	32.3
	0.50	0.7732	23.6

Analysis Plan

Summary statistics will be provided for continuous variables and frequency tables will be used to summarize categorical variables. We will estimate the overall response rate, along with the Bayesian 95% credible interval. Kaplan-Meier method will be used to estimate overall survival, time to treatment and progression-free survival. The two-sided log-rank tests will be used to assess the differences of time-to-event outcomes between subgroups of patients. Logistic regression analyses will be used to explore the association between biomarker and response or resistance to therapy.

Data from all subjects who receive any study drug will be included in the safety analyses. Subjects who entered the study but did not take any of the study drug and had this confirmed will not be evaluated for safety. The severity of the toxicities will be graded according to the NCI CTCAE v4.03 whenever possible. We will follow standard reporting guidelines for adverse events. Safety data will be summarized by category, severity and frequency.

12. Adverse Events and Reporting Requirements

Adverse event reporting will be as per the current NCI criteria and the Leukemia-specific Adverse Event Recording and Reporting Guidelines (Appendix D) . The descriptions and grading scales found in the revised NCI Common Terminology Criteria for Adverse Events (CTCAE) version 4.03 will be utilized for adverse event reporting.

<http://ctep.cancer.gov/reporting/ctc.html>

A. Adverse Events

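### Section 12.A conflicts with Sections 8 and 13.G on what goes on the CRF; if 12.A is followed, graded cytopenia rates and the counts behind CRp are not available there

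*Combined protocol and SAP*

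**What the plan says.** Three sections of the protocol set rules for CRF content.

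- Section 8 (Study Procedures): "Results of all assessments will be recorded on the appropriate CRF". Table 7 lists hematology as a scheduled assessment from screening through follow-up: "Includes WBC with differential, hemoglobin, platelet".
- Section 12.A (Adverse Events): "adverse events and protocol specific data will be entered into PDMS/CORe", and that system is the electronic CRF. The section then restricts CRF adverse events to those both unexpected and related to study drug. It lists the cytopenias among expected events (item 1c) and ends with item 3(d): "abnormal hematologic values will not be recorded on the CRF". The same item requires the worst Grade 3 or 4 chemistry value per course to be reported on the CRF.
- Section 13.G requires every adverse event after exposure to daratumumab, serious or not and related or not, to be entered on the CRF.

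Two other routes bypass the CRF rule. Section 12.B requires all serious adverse events to be reported whether or not expected or attributed. Section 13.B makes daratumumab-related cytopenias of Grade 4 or higher events of special interest, recorded on a serious adverse event form.

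The data are needed in two places. Section 9 defines response partly by blood counts, and the Analysis Plan in Section 11 states: "Safety data will be summarized by category, severity and frequency".

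**The concern.** Site staff cannot enter all assessment results and all adverse events while also leaving out abnormal counts and expected events. Table 7 sends staff to Section 12 for adverse-event instructions, so 12.A may well be the rule followed in practice.

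Safety and tolerability is a secondary objective, and 12.A itself lists myelosuppression as expected during leukemia therapy. A safety summary drawn from a CRF kept under 12.A would omit most cytopenias. A reader could then not tell whether they were rare or simply not collected.

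On the efficacy side, low counts separate CRp from CR and define the starting point for hematologic improvement (HI). If they are not on the CRF, those categories cannot be checked from the trial database.

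**Working it through.** The plan gives no figure to reproduce. The check sets the rules side by side and then traces which analyses need the affected data.

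**1. The rules compared**

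| Data item | Section 8 with Table 7 | Section 13.G | Section 12.A |
|---|---|---|---|
| Scheduled blood count, abnormal | On CRF | Not addressed | Off CRF (3d) |
| Non-serious expected cytopenia as an adverse event | Not addressed | On CRF | Off CRF (1c and the restriction to unexpected related events) |
| Grade 3-4 chemistry value | On CRF | Not addressed | Worst value per course on CRF (3d) |

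The first two rows contradict each other across sections. The third shows that 12.A does provide for laboratory values in chemistry, with no equivalent for blood counts.

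**2. Safety, under both readings of item 3(d)**

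- Read as a rule about laboratory values, it leaves no abnormal counts on the CRF, so cytopenias cannot be graded from it.
- Read as a rule about adverse-event entry only, it lets counts reach the CRF through Section 8. Item 1(c) and the restriction to unexpected related events still keep non-serious cytopenias out as adverse events. The Analysis Plan does not say that cytopenias will be graded from laboratory values instead.

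Under 12.A, what remains is cytopenias reported as serious events and daratumumab-related ones of Grade 4 or higher. These routes miss non-serious Grade 3 cytopenias, and non-serious Grade 4 cytopenias attributed only to venetoclax or to disease.

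**3. Response categories and counts (Sections 9 and 11)**

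- CRp: "Complete remission without platelet recovery (CRp): As per CR but platelet count" below 100 × 10⁹/L. This is the one primary-endpoint category that requires a low count by definition.
- CR: "The patient must be free of all symptoms related to leukemia and have an absolute neutrophil count" of at least 1.0 × 10⁹/L, with platelets of at least 100 × 10⁹/L. Item 3(d) removes these values only if they meet the threshold yet lie outside the laboratory's normal range. The protocol gives no range.
- PR: the first part builds on CR. The second, a 50% fall in marrow blasts, can be read as needing no counts.
- Morphologic leukemia-free state (AML only) and marrow CR (MDS only): no counts needed.
- HI starts from a low baseline, for example "For patients with pretreatment hemoglobin less than 11 g/dL, greater than 2 g/dL increase in hemoglobin". Platelet and neutrophil HI start below 100 and 1.5 × 10⁹/L. HI is not in the primary endpoint and has no named analysis.

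So three of the five primary-endpoint categories refer to counts, but only CRp needs an abnormal one.

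**4. Effect on overall response**

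An AML patient with under 5% blasts still counts through morphologic leukemia-free state. An MDS patient with 5% blasts or fewer and at least a 50% fall still counts through marrow CR. T-ALL/T-LBL has neither category, so a low neutrophil count could decide responder status there unless the second part of PR stands alone. The plan intends at least 10 T-ALL patients of up to 36: 10/36 = 27.8%. That is a share of enrollment, not a misclassification rate.

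**5. Monitoring**

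The toxicity stopping rule in Section 11 counts only non-hematologic events, so Table 5 does not depend on the missing data.

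**The case against.** The best answer is that item 3(d) is only an adverse-event rule. It sits under the Adverse Events heading, in a list of expected events, and its companion sentence uses toxicity grades. Section 12.A names adverse events and protocol-specific data as separate content. Table 7 states when data go only to the medical record, as for most concomitant medications, and says nothing of the kind for hematology. Entering normal counts while omitting abnormal ones would be an odd instruction.

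This has force as a reading of intent but does not settle the matter. Item 1(c) already covers cytopenias as expected events, so 3(d) adds little as an adverse-event rule. Its wording concerns values and makes no exception for counts used in response. Even on this reading, the conflict with 13.G remains and cytopenias stay off the CRF as adverse events.

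A reader might infer that response and all hematologic toxicity cannot be derived from the trial data at all. The documents do not support that. No section says response must be computed from CRF counts, and an investigator-assessed category could be entered; the plan neither confirms nor excludes this. Source counts remain in the medical record. The serious-event and special-interest routes capture some cytopenias, and following 13.G would bring in all those reported as adverse events.

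Appendix D, which Section 12 cites for adverse-event recording, is not in the text available for this review and may bear on how 3(d) is applied.

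**Conclusion.** The contradiction between 12.A and Sections 8 and 13.G stands and should be resolved. The main consequence is for safety: if 12.A is followed, laboratory-graded cytopenia rates cannot be produced from the CRF beyond events reported as serious or as daratumumab-related Grade 4 or higher. The second is for verification: the counts behind CRp, and less directly CR, PR and HI, are not on the CRF.

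The effect on the overall response rate is probably small. It could matter mainly in T-ALL/T-LBL, and there only if PR's 50% blast reduction is not a criterion in its own right. No monitoring boundary changes.

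The conclusion assumes that sites follow 12.A where the sections differ, that a platelet count below 100 × 10⁹/L is treated as abnormal, and that Appendix D does not already resolve the conflict.

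**What to change.** 1. Reconcile Section 12.A (the restriction to unexpected related events, item 1c and item 3d) with Sections 8 and 13.G, so that one rule states which adverse events go on the CRF.
2. Reword item 3(d) so that it only exempts abnormal counts from entry as individual adverse events.
3. State that neutrophil, hemoglobin and platelet values from the Table 7 hematology draws are captured on the CRF as laboratory data.
4. Add to the Analysis Plan that Grade 3-4 cytopenias will be summarized from those values.

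The cost is protocol wording and data entry; the blood is already drawn. For a patient treated for a full year (13 cycles of 28 days), Table 7 gives 2 × 4 + 4 × 2 + 7 × 1 = 23 treatment draws, plus screening and end of treatment, or 25. At the maximum of 36 patients that is 36 × 25 = 900 draws with three values each, before the monthly follow-up draws in responders. Earlier discontinuation lowers this total. No new tests are needed.
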